6.6 Missing Data

Given the strong plans for participant follow-up as part of the main study REPRIEVE, it is anticipated that missing data will be minimal. Missing data will be assumed to be missing at random. For participants lost to follow-up, the available outcome data until the time of loss to follow-up will be used. The amount of and reasons for missing evaluations of outcome measures and drop-out will be examined by treatment group. However, the longitudinal analysis of primary physical function outcome will be robust in the event of uneven participant drop-out related to the rate of decline in physical impairment.

6.7 Statistical Significance Level

Statistical comparisons of the primary outcome measures between treatment groups will be performed as two-sided at 5% Type I error.

Given the multiple primary hypotheses and the various secondary outcomes outlined, it is recognized that there is a multiplicity of analyses to be performed, which leads to an increased probability that at least one of the comparisons could be "significant" by chance. Although the overall level of significance for all treatment comparisons will be 5%, we will be conservative in the interpretation of the secondary and supporting analyses, taking into account the degree of significance, and looking for consistency across outcomes.

7 STUDY POPULATION

To describe the study population, the below baseline [REPRIEVE entry] information will be summarized.

The variables will be summarized as continuous, categorical or both, as indicated below. The tables will provide the number of participants, mean and standard deviation, median (Q1 – Q3), P10 – P90, minimum – maximum (referred to as statistics in the listings below) for continuous measures, and number (%) for categorical measures. In calculation of percentages, participants with missing data will be excluded from the denominator.

The baseline summaries will be provided by the following.

- 1) Overall and by treatment group.
- 2) By prospective vs. retrospective enrollment (enrolled into PREPARE before vs. after initiation of study treatment in REPRIEVE).
- 3) By co-enrollment into A5333s (i.e. participants with vs. without CT scans) and treatment group.

Summaries by treatment group will use randomized treatment group.

For categorical variables, Chi-squared test (all cells have at least 5 expected counts) or Fisher's Exact Test (at least one cell has less than 5 expected counts) will be used to compare prospective vs. retrospective enrollees (#2 above) and those enrolled vs. not enrolled into A5333s (#3 above). Wilcoxon rank sum tests will be used for continuous variables. Since treatment allocation was randomized and double-blinded in REPRIEVE, no statistical tests will be provided for the summaries by treatment group.

Demographic and behavioral variables:

Variable	Summary	Details
Age (years)	Statistics Number (%)	Age at REPRIEVE entry. By category: 40-49, 50-59, 60-69, 70-75 years.
Sex	Number (%)	Defined as sex at birth.
Race	Number (%)	
Ethnicity	Number (%)	
Race/ethnicity	Number (%)	
Menopausal status	Number (%)	Limited to women.
Weight (kg)	Statistics	
BMI (kg/m ²)	Statistics Number (%)	Calculated as weight (kg)/height(m) ² . By category: as underweight (<18.5), normal (18.5-24.9), overweight (25-29.9), obese (≥30).
Smoking status	Number (%)	By category: current; former; never.
Total years smoked	Statistics	Limited to former/current smokers.
Alcohol use	Number (%)	By category: yes/no, defined as: yes = sometimes or often drink 1-2 alcoholic drinks a day; no = rarely/never.

HIV-related variables and ART regimen:

Variable	Summary	Details
Nadir CD4 (cells/mm ³)	Statistics	By category: <50; 50-99; 100-199; 200-349; 350-499; ≥500; Unknown.
CD4 (cells/mm ³)	Statistics Number (%)	
HIV-1 RNA (copies/ml)	Number (%)	By category: 50-199, 200-349, 350-499, 500-649, 650-799, ≥800.
ART regimen	Number (%)	By category: <50; ≥50.
ART duration (years)	Statistics Number (%)	Limited to those with quantifiable HIV-1 RNA, if substantial number
		By class (NRTI+NNRTI, NRTI+PI, NRTI+INI, Other NRTI-containing, NRTI-sparing) and regimen.
		By category: <10; ≥10.

Co-morbid conditions:

Variable	Summary	Details
Years since HIV diagnosis	Statistics	
History of AIDS	Number (%)	
HBV/HCV	Number (%)	
Hypertension	Number (%)	
Diabetes mellitus	Number (%)	
Cancer	Number (%)	
Chronic kidney disease	Number (%)	
Family history of CVD	Number (%)	

8 EFFECT OF PITAVASTATIN ON PHYSICAL FUNCTION

This section outlines analyses for the outcomes addressing the primary objective 1.2.1, secondary objectives 1.3.4, 1.3.5 and exploratory objective 1.4.3 (see Section 3).

8.1 Analysis Considerations

The analyses of physical function outcomes will be ITT, as defined in Section 6.5.

Descriptive statistics (number of observations, mean and standard deviation, median (Q1 – Q3), P10 – P90, minimum – maximum) for numerical outcomes, number (%) for categorical outcomes and ordinal outcomes with limited scale (e.g. frailty with 3 ordered categories), and graphical presentations will be examined at REPRIEVE entry and over time. PREPARE entry evaluations performed after the start of REPRIEVE study treatment will not be used for REPRIEVE entry in these summaries.

8.2 Primary Analysis of the Chair Rise Rate

8.2.1 Analysis Data

All available outcome data regardless of participants time of entry into PREPARE (i.e. including both, PREPARE entry evaluations performed prior to and after REPRIEVE study treatment initiation) and regardless of visit windows. Participants without pre-treatment chair rise rate will be included.

8.2.2 Analytic Methods

Linear mixed effects model will be used, with time modeled on a continuous scale, where REPRIEVE entry is time 0. The primary model will include intercept, the main effect of time and the interaction of time and treatment group, and omit the main effect of treatment group (intercept). It takes advantage of the fact that randomized group allocation in REPRIEVE means that there is no underlying difference in physical function between treatment groups at REPRIEVE entry and will be the most powerful

In the event of non-linear change in outcome over time, alternative transformations of the outcomes or time axis will be assessed. If such transformations are not feasible, modeling will be performed using an arbitrary time effect (i.e., time modeled as a factor on four levels). The treatment effect of interest for the primary treatment group comparison will be the average difference across post-baseline time points; an interaction of treatment and time will also be assessed and secondary comparisons by year will also be presented.

8.3 Subgroup Analyses of Chair Rise Rate

These primary analyses will be extended to evaluate subgroup effects of treatment, namely different treatment effects by

- race (white vs non-white),
- sex,
- baseline CD4 cell count (<350 cell/mm³ vs. \geq 350 cells/mm³),
- ART duration (<10 or \geq 10 years),
- baseline physical function deficits (mSPPB <10 vs. \geq 10),
- baseline systemic inflammation (by tertile of IIS).

The basic model will include intercept, the main effects of time and subgroup and the interaction of time and subgroup, i.e. incorporating potential differences between subgroups both, in baseline chair rise rate, and in rate of change per year. To evaluate subgroup effects of treatment, inclusion of the interaction of

time and treatment group, and the interaction of time, treatment group and subgroup will be considered. The primary parameter of interest is the difference in the rate of change (slope) between placebo and pitavastatin over time between the levels of a subgroup variable (i.e., the interaction between treatment, time and subgroup). Each subgroup analysis will be conducted separately. The model will not be extended to include multiple subgroup variables.

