6.3.1.4 Gait Speed

Walking is a complex task requiring balance, mobility, strength, and coordination. In many functional performance batteries, including the mSPPB, timed walking is an integral component. It is an excellent predictor of lower extremity function and is well correlated with falls and fractures resulting from falls; it also is a strong predictor of disability and mortality. Two measurements of usual gait speed on a 4-meter course will be obtained. (See MOPS for further details.)

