10.2.2 Secondary Outcome Measures

10.2.2.1 Secondary physical function outcome measures assessed annually for **60** months.

Raw scores for each of the additional components of the SPPB (grip strength, gait speed, ability to hold the one leg stand for 30 seconds) as well as the composite SPPB score (composite scoring of chair stand, balance, and gait) measured annually to month **60**.

Physical function deficits defined as a composite SPPB score ≤ 10 assessed annually to month **60** [124,125].

Frailty (classified as non-frail, pre-frail, and frail) as well as the frequency of its components (exhaustion, weight loss, low activity, slow walk, grip strength) and the number of frailty components present [126].

Self-reported physical activity via two questions measured on a three-point ordinal scale on the REAP assessment.

10.2.2.2 Secondary outcome measures for the mechanistic objective quantified at REPRIEVE (A5332) entry and 12 months

Serum concentrations of each individual biomarker of the IIS (IL-6, sTNFR-1) as well as other biomarkers implicated in the pathogenesis of physical function impairment (these may include markers such as sTNFR-2, IP-10, IGF-1, TGF- β 1) or those that may mediate the effects of statin treatment on systemic inflammation (CMV IgG).

The specific list of biomarkers of interest may be modified closer to the time of analysis based on the identification of additional biomarkers or pathways involved in this process.

10.2.2.3 Secondary outcome measures for the mechanistic objectives related to fatty infiltration of the skeletal trunk muscles assessed at REPRIEVE (A5332) entry and 24 months:

Shoulder and upper back muscle density measured in HU.

Paraspinal and trunk muscle volume (area).

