10.6.1 Effects of Pitavastatin on Physical Function

Descriptive statistics (median, Q1, Q3, P10, P90, min, max) and graphical presentations of each component of the SPPB, its composite score as well as the prevalence of physical function deficits (SPPB \leq 10) will be examined at REPRIEVE (A5332) entry and over time. A5361s entry evaluations performed after the start of REPRIEVE (A5332) study treatment will be excluded from these summaries.

Analyses of chair rise rate will use linear mixed effects models with time modeled on a continuous scale, where REPRIEVE (A5332) entry is time 0.

The primary parameter of interest will be the difference in the rate of change (slope) between placebo and pitavastatin over time (i.e., the interaction between treatment and time). The primary analysis will include available measured outcomes (including those obtained at REPRIEVE [A5332] entry) in the outcome

vector and will omit the treatment group main effect (intercept) from the model. This approach allows for variable evaluation time and inclusion of data for all participants regardless of their time of entry into A5361s. It takes advantage of the fact that randomized group allocation in REPRIEVE (A5332) means that there is no underlying difference in physical function between treatment groups at REPRIEVE (A5332) entry and will be the most powerful [131]. Further, the analysis will be robust in the event of uneven participant drop-out related to the rate of decline in physical impairment. In the event of non-linear change in outcome over time, we will first assess alternative transformations of the outcomes or time axis. If such transformations are not feasible, modeling will be performed using an arbitrary time effect (i.e., time modeled as a factor on four levels). In this case, the treatment effect of interest for the primary treatment group comparison will be the average difference across post-baseline time points; an interaction of treatment and time will also be assessed and secondary comparisons by year will also be presented. It is noted that the power of the study to detect a comparable effect size is reduced under this alternative modelling framework.

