These primary analyses will be extended to evaluate subgroup effects of treatment, namely different treatment effects by race (white vs non-white), sex, baseline CD4 cell count (<350 cell/mm vs. \geq 350 cells/mm), ART duration (categorized as <10 or \geq 10 years), physical function deficits at REPRIEVE (A5332) entry (SPPB \leq 10 vs. $>$ 10), and systemic inflammation (by tertile of IIS) at REPRIEVE (A5332) entry. Sensitivity analyses excluding participants who enrolled into A5361s after REPRIEVE (A5332) entry will also be performed.

Given the expected discretized distribution of the remaining SPPB outcomes (including the overall composite score), longitudinal analyses for these measures as well as the self-reported physical function outcomes from the REAP assessment will use the methods of Wei and Johnson to provide an overall assessment of treatment group differences between the groups over time.

The prevalence of the frailty phenotypes and their components over time and by treatment group will be described. Treatment group differences in the prevalence of the frailty phenotype (non-frail, pre-frail, frail) will be assessed via marginal modeling with a cumulative logit using generalized estimating equations.

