4.2 Secondary Outcome Measures

4.2.1 *Physical Function and Activity Secondary Outcome Measures*

All physical function outcome measures are assessed annually over 48 months (see Section 5), unless otherwise specified below.

Short Physical Performance Battery (SPPB) Outcome Measures [1.2.1]:

- Composite SPPB score (composite scoring of repeated chair stand, balance, and gait speed) (*Guralnik et al. J Gerontol. 1994 Mar; 49(2):M85-94.*) For gait speed, faster of the two results (minimum) will be used.
- Physical function deficits defined as a composite SPPB score <10.

Modified Short Physical Performance Battery (mSPPB) Outcome Measures [1.2.1]:

- Composite mSPPB score, modified slightly from Simonsick et al (*J Gerontol A Biol Sci Med Sci* (2001) 56 (10): M644-M649). The composite score (ranging from 0 to 3) defined as a sum of the following 3 components.
 - Chair rise rate (stands/second), as above, divided by maximal possible performance to derive a ratio between 0 to 1 (1 chair stand/second shown by previous studies will be used as the maximal possible performance unless suggested otherwise by the data).
 - Total standing balance time, as the sum of time to hold each of 3 stands (semi-tandem, tandem, and one-leg), divided by 90 (the allotted time of 30 seconds per each stand) to derive a ratio between 0 to 1.

- Gait speed (meters/second) divided by the maximal possible performance to derive a ratio between 0 to 1 (2 meters/second shown by previous studies will be used as the maximal possible performance unless suggested otherwise by the data).
- Balance defined as ability to hold one leg stand for 30 seconds and as a ratio as defined above.
- Gait speed (meters/second) evaluated by time to complete a 4-meter walk. Average of the two results will be used.

Frailty Outcome Measures [1.2.1]:

Assessment of frailty is based on presence of the following criteria: (1) weight loss, (2) exhaustion, (3) low physical activity, (4) slow walk, (5) weak grip strength as described by Fried et al (*J Gerontol A Biol Sci Med Sci*. 2001 Mar;56(3):M146-56.). For gait speed and grip strength, average of the results will be used.

- Frailty classified as non-frail (no criteria present), pre-frail (1 – 2 criteria present), and frail (≥ 3 criteria present).
- Number of frailty components present.
- Presence of each frailty component (weight loss, exhaustion, low physical activity, slow walk, weak grip strength).

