6 GENERAL ANALYSIS CONSIDERATIONS

6.1 Baseline

Baseline will be defined as the REPRIEVE entry evaluation. The baseline characteristics derived for the main study REPRIEVE will be used, if available. For the physical function and frailty measures, baseline is defined as PREPARE entry evaluation prior to or on the day of the study treatment initiation in REPRIEVE. As such, participants who enroll into PREPARE after initiation of study treatment in REPRIEVE, will not have a baseline (pre-treatment) evaluation.

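### The SAP's baseline-deficit subgroup is cut at mSPPB 10 on a scale that stops at 3, and reading it as SPPB still leaves <10 in the SAP against ≤10 in the protocol

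*SAP*

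**What the plan says.** SAP 8.3 extends the primary chair-rise model to six subgroup variables. One is "baseline physical function deficits (mSPPB <10", with 10 or above as the other level. The parameter of interest is the treatment by time by subgroup interaction.

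SAP 4.2.1 defines two different composites:

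- For the mSPPB: "The composite score (ranging from 0 to 3) defined as a sum of the following 3 components". The components are chair rise rate, standing balance time and gait speed, each scaled to lie between 0 and 1.
- For the SPPB: "Physical function deficits defined as a composite SPPB score <10".

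The protocol uses the SPPB with a different boundary in three operative places:

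- Secondary outcome (10.2.2): "Physical function deficits defined as a composite SPPB score ≤ 10 assessed annually".
- Descriptive summaries (10.6.1): "its composite score as well as the prevalence of physical function deficits (SPPB", followed by ≤10.
- Subgroup (10.6.1): "physical function deficits at REPRIEVE (A5332) entry (SPPB", followed by ≤10 against >10.

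In the protocol's section on evaluations, mSPPB is the name of the test battery (6.3.1.4: "In many functional performance batteries, including the mSPPB, timed walking is an integral component"). SAP 6.1 adds that "participants who enroll into PREPARE after initiation of study treatment in REPRIEVE, will not have a baseline (pre-treatment) evaluation", so this subgroup can be formed only among participants enrolled before starting study treatment.

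**The concern.** There are two separate faults. The first is a cut point that lies outside the range of the score it is applied to, so the rule cannot divide anyone. The second remains after the obvious repair of the name: the two documents put a score of exactly 10 on opposite sides of the line.

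Baseline physical function is a named effect modifier in exploratory objective 1.4.3. It also reflects an idea in Protocol 2.2, that a statin's effect may depend on where a person stands on the functional trajectory when treatment starts. The same deficit definition is a secondary outcome in its own right, so the reported prevalence over time would depend on which document the analyst followed. If the cut-off is reconciled only after results are available, the subgroup can no longer be called prespecified.

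**Working it through.** **Step 1. Can the mSPPB reach 10?** Inputs are from SAP 4.2.1.

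- Chair component: stands per second ÷ 1, between 0 and 1.
- Balance component: seconds held ÷ 90, between 0 and 1.
- Gait component: metres per second ÷ 2, between 0 and 1.

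Maximum = 1 + 1 + 1 = 3. This reproduces the SAP's own range of 0 to 3. Since 3 < 10, the lower level contains every participant with a baseline score and the upper level contains none. The subgroup factor has a single level, so its interaction with treatment and time cannot be estimated.

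The SAP allows the maximal performance values to be revised from the data. That does not help, because each component remains a ratio from 0 to 1. Even if the cap were ignored and two components stood at 1, the third would have to equal 10 − 2 = 8. That means 8 chair stands per second, or a gait speed of 8 × 2 = 16 m/s.

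**Step 2. What was probably meant?** Three features point to the SPPB. The protocol's matching subgroup names it. The SAP defines the term physical function deficits on it, with the same <10. The protocol uses mSPPB as the name of the battery. This is an inference, though a well-supported one.

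**Step 3. Does the corrected name resolve the cut-off?** Compare the rules score by score.

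| SPPB score | SAP rule (<10) | Protocol rule (≤10) |
|---|---|---|
| 9 or below | deficit | deficit |
| exactly 10 | no deficit | deficit |
| 11 or above | no deficit | no deficit |

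The rules differ only at 10. The conflict sits in two places in the SAP (4.2.1 and 8.3) and three in the protocol's outcome and analysis sections (10.2.2 once, 10.6.1 twice). Protocol 2.2 also gives ≤10 as the definition of impairment in a cited cohort, but that is background and is not counted.

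**Step 4. Could a symbol have been lost in reading the PDF?** This is unlikely. SAP 8.3 pairs <10 with its exact complement ≥10, and SAP 4.2.1 repeats <10. The other five subgroup definitions in SAP 8.3 agree with Protocol 10.6.1.

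**Step 5. How many participants would move?** The documents do not give the share scoring exactly 10. Purely as an assumption, with all 600 participants contributing a score:

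| Assumed share at exactly 10 | Participants reclassified |
|---|---|
| 5% | 600 × 0.05 = 30 |
| 10% | 600 × 0.10 = 60 |
| 15% | 600 × 0.15 = 90 |
| 20% | 600 × 0.20 = 120 |

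For the subgroup, the number at any given share would be lower, because participants who enrolled after starting treatment have no baseline score.

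**The case against.** The best defence is that this is an editorial slip the SAP itself resolves. The subgroup's label is a term that SAP 4.2.1 defines on the SPPB with the same <10. An analyst would follow that definition, and anyone who did not would see a one-level factor at once, so no misleading estimate would be produced. The SAP also states its boundary consistently in both places. Protocol 10.6 describes its own text as an overview and leaves the full plan to the SAP, so <10 may fairly be called prespecified. SAP 1 further leaves coding details to a separate implementation plan. The reach is small: an exploratory subgroup and one secondary outcome, with the composite SPPB also analysed without any cut-off.

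Much of this stands. The wrong name would probably be noticed, the reach is limited, and the risk of choosing the cut-off after seeing results arises only if the conflict is left unresolved until then.

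It does not remove the point. An implementation plan would have to contradict the text of SAP 8.3 to make the subgroup workable. Nothing in either document says which cut-off prevails, or why the SAP departs from the protocol. SAP 3 says its design section rests on protocol Version 1.0, a clarification memo and a letter of amendment, none of which was available here. A deliberate choice of <10 therefore cannot be excluded, and the remedy has to allow for it.

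**Conclusion.** The concern holds on both parts. As written, the SAP 8.3 split puts all participants with a baseline score in one level and none in the other, so the interaction it names cannot be estimated. With the name corrected to SPPB, the SAP and protocol still disagree for every participant scoring exactly 10. The number affected is unknown; the 30 to 120 in the working rests entirely on assumed shares of 600 and, for the subgroup, overstates the number at any given share.

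The consequence is bounded. It touches one exploratory subgroup (objective 1.4.3) and one secondary outcome. The same cut would apply to both arms, so the discrepancy does not by itself bias the treatment comparison. The primary chair-rise slope analysis is not affected. The plan should be corrected, because one listed analysis cannot be run as written and one outcome has two definitions.

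The arithmetic on the 0 to 3 range needs no assumption. That mSPPB was meant to be SPPB is an inference from the surrounding text.

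**What to change.** Before unblinding:

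1. In SAP 8.3, replace mSPPB with the composite SPPB and split at ≤10 against >10, as in Protocol 10.6.1.
2. In SAP 4.2.1, change the deficit definition to SPPB ≤10, as in Protocol 10.2.2.
3. If the team intended <10, keep it, state the reason, and align the protocol's secondary outcome, summaries and subgroup to it.

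The first route costs two SAP edits. The alternative needs the name corrected in SAP 8.3, a recorded reason, and changes at three places in the protocol. Neither route needs new data or an extra analysis.
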